4.8.2. Progression Free Survival

PFS is defined as the time from C1/D1 to the first occurrence of progression or death from any cause, whichever occurs first, per RECIST v1.1 and irRC as determined by the investigator. PFS (in months) is calculated as (death or censor date – date of C1/D1 + 1) / 30.4375.

Rules for progression or censoring are described in Table 4-1. Patients who are not known to have progressed prior to analysis cut-off date will be censored at the date of last adequate tumor assessment or clinical cut-off, whichever comes first.

Table 1 PFS analyses and censoring rules.

Situation	Date of Progression or Censoring	Outcome
Incomplete or no baseline tumor assessment	C1/D1 date	Censored
Documented progression (per RECIST 1)	Earliest date on which radiological progression is documented	Progressed
Death	Date of death	Progressed
No progression	Date of last adequate tumor assessment with no documented progression	Censored
Treatment discontinuation	Date of Treatment discontinuation	Progressed

A summary of the number and percentage of patients experiencing a PFS event, and the type of event (progression or death) will be provided along with median PFS. A Kaplan-Meier plot of PFS will be presented by pool dose.

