11.1.6 Duration of Response

Duration of overall response: The duration of overall response is measured from the time measurement criteria are met for CR/PR or iCR/iPR (whichever is first recorded) until the first date that recurrent or progressive disease is objectively documented (taking as reference for progressive disease the smallest measurements recorded since the treatment started).

The duration of overall CR is measured from the time measurement criteria are first met for CR until the first date that progressive disease is objectively documented.

Duration of stable disease: SD is measured from the start of the treatment until the criteria for progression are met, taking as reference the smallest measurements recorded since the treatment started, including the baseline measurements.

11.1.7 *Progression-Free Survival*

PFS is defined as the duration of time from start of treatment to time of progression or death, whichever occurs first.

11.1.8 *Response Review*

Radiological images will be collected for a possible review of response by an expert(s) independent of the study. Measurement of tumor response by a trained radiologist/nuclear medicine physician at each clinical site will be chronicled and reported unless or until a central expert review takes place.

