2.5. Efficacy, Pharmacokinetic, and Safety Variables

2.5.1. Efficacy Variables

- Objective Response Rate (ORR) defined as the percentage of patients who have at least one confirmed partial response (PR) or complete response (CR) according to Response Evaluation Criteria in Solid Tumors (RECIST) v.1.1
- Disease Control Rate (DCR) defined as the percentage of patients with a response of CR, PR or stable disease (SD) according to RECIST v.1.1
- Progression Free Survival (PFS) defined as the time from the first study treatment to the first occurrence of progression, as measured by RECIST v.1.1 or death from any cause, whichever occurs first
- Overall survival (OS) defined as the time from first study treatment to death from any cause.
- Duration of stable disease (DOSD) defined as the time from the first occurrence of stable disease or better (PR or CR or SD) to the time of the first documented disease progression or death from any cause, whichever occurs first per RECIST v.1.1

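### The PFS formula in SAP 4.8.2 repeats the OS formula and omits the progression date, contradicting the section's own definition and Table 1

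*SAP*

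**What the plan says.** SAP 4.8.2 opens with the definition: "PFS is defined as the time from C1/D1 to the first occurrence of progression or death from any cause, whichever occurs first". The next sentence is the only calculation rule for PFS in the SAP. It begins "PFS (in months) is calculated as (death or censor date", then subtracts the date of C1/D1, adds 1 and divides by 30.4375. It uses a death date or a censor date and nothing else.

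The following paragraph sends the reader to the date rules: "Rules for progression or censoring are described in Table 4-1". The table is captioned Table 1. There, a patient with documented progression takes "Earliest date on which radiological progression is documented" and is counted as progressed, and a patient who dies takes the date of death. The text censors only patients not known to have progressed. The section closes by asking for PFS events to be counted by type, progression or death.

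The other definitions agree with the first sentence of 4.8.2. SAP 2.5.1 has PFS as "the time from the first study treatment to the first occurrence of progression", or death if that comes first. Protocol 11.1.7 says "PFS is defined as the duration of time from start of treatment to time of progression or death, whichever occurs first".

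Two neighbouring formulas are useful for comparison. The OS formula in SAP 4.8.3 is the same expression as the PFS formula, term for term. The formula for duration of stable disease (DoSD) in SAP 4.8.4 starts from an event date or a censor date.

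**The concern.** A formula is what a programmer is most likely to code. This one has no place for the event that ends PFS in a patient who progresses. Because it matches the OS formula exactly, it looks like text carried over from OS. It does not look like a deliberate change: SAP Section 5 lists the departures from the protocol, and a redefinition of PFS is not among them.

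If the formula were coded alone, two groups of progressed patients would be mishandled. Those who later die would be given their overall survival time. Those still alive would have neither a death date nor, under the section's own rules, a censor date. Protocol 6.6 continues survival follow-up every 12 weeks after progression, so later death dates should be in the data and available to be picked up. The results exposed are the PFS quartiles, including the median, the rates at 3, 6, 9, 12, 18 and 24 months (SAP 4.8), and the Kaplan-Meier plot.

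**Working it through.** The documents give no event count, target or power for PFS, so there is no planned figure to reproduce. The check sets the rules side by side and then runs both on one illustrative patient.

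**Which date each rule uses**

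| Patient | Definition and Table 1 | Formula read literally |
|---|---|---|
| Progresses, later dies | Progression date | Death date, so PFS = OS |
| Progresses, still alive | Progression date | No death date and no censor date, so no value |
| Dies without documented progression | Death date | Death date |
| Neither event | Last adequate tumour assessment | Same censor date |

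The formula fails only for patients with documented progression. The rows assume a complete baseline tumour assessment, since Table 1 censors the others at C1/D1.

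**Inputs**

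- Month divisor: 30.4375 = 365.25/12 (SAP 4.2.11). This checks exactly.
- Progression 63 days after C1/D1. This is 9 weeks, the time of the first scheduled response assessment (protocol 11.1).
- Death 180, 300 or 540 days after C1/D1. These are assumed values chosen to show a range.

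**With the Table 1 date**

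PFS = (63 + 1)/30.4375 = 2.10 months, whatever happens later.

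**With the formula read literally**

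| Death after C1/D1 | Calculation | PFS by formula | Landmarks at which the patient counts as progression-free |
|---|---|---|---|
| 180 days | 181/30.4375 | 5.95 months | 3 months |
| 300 days | 301/30.4375 | 9.89 months | 3, 6 and 9 months |
| 540 days | 541/30.4375 | 17.77 months | 3, 6, 9 and 12 months |
| Alive | none possible | no value | none |

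Under Table 1 the same patient fails before the 3-month landmark in every case. For a patient who dies, the excess is the time from progression to death; at 300 days it is (300 − 63)/30.4375 = 7.79 months.

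**Direction.** For progressed patients who die later, the error can only lengthen PFS. For progressed patients who are alive, the value is missing, and the effect on the median depends on how the missing value is then handled. The net effect on the summary is therefore not determined by the documents.

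**The case against.** The strongest defence is that the section taken as a whole is clear. The definition comes immediately before the formula, the date table follows it, and events must be reported as progressions or deaths, which cannot be done if only deaths supply event dates. SAP 2.5.1 and protocol 11.1.7 point the same way. An analyst who reads all of 4.8.2 would use the progression date. This stands, and it limits the conclusion: a reader might infer that the SAP specifies PFS as time to death, or that reported PFS will be inflated, and the documents support neither. What remains is that the one explicit formula disagrees with everything around it, and the pointer to the governing table carries the wrong number.

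A reader might also infer that DoSD has the same error, because SAP 4.8.4 says it is censored in the same way as PFS. It does not. That section has its own formula, built on the event or censor date, and ends DoSD at documented progression or death. It borrows only the censoring rules, not the faulty PFS expression.

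Finally, the stakes are modest. Protocol Table 2 makes PFS secondary; the primary endpoints concern safety and, in Phase 2a, ORR. Protocol 15.5.1 plans descriptive statistics, SAP 4.2.5 reports no p-values, and no decision rule depends on PFS. This also stands, and it bears on priority. It is not a reason to leave a wrong rule in place.

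**Conclusion.** The contradiction is real. The only PFS calculation rule in the SAP omits the progression date and cannot be applied as written to a patient who has progressed. Read literally, it gives the illustrative patient 5.95 to 17.77 months instead of 2.10 if the patient dies, and no value if the patient is alive. PFS medians and the 3- to 24-month rates could therefore be wrong if the formula is coded on its own; they would be right if the analyst follows Table 1.

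The size rests on an invented patient: the 63 days come from the assessment schedule, and the death times are assumed. No trial data enter the calculation. The finding concerns the formula's wording. The divisor and the added day are correct, and neither DoSD nor any primary endpoint is affected.

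**What to change.** Replace the formula in SAP 4.8.2 with:

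PFS (months) = (date of first PFS event, or censor date per Table 1 if there is no event, − date of C1/D1 + 1) / 30.4375, where a PFS event is documented progression or death, whichever is earlier.

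This brings the formula into line with the construction already used for DoSD. Do not write it as the earliest of progression, death and censor date. The last clean scan precedes a later progression or death, so taking the minimum of the three could return the censor date for a patient who had an event.

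Correct the text reference from Table 4-1 to Table 1. SAP 4.8.3 has the same slip, citing Table 4-2 for a table captioned Table 2.

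One related item needs its own decision. The last row of Table 1 counts treatment discontinuation as progression, which the PFS definition does not. The formula above follows the definition; if that row is kept, the event list in the formula must name it.

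The cost is one SAP line and the table references. If PFS outputs already exist, confirm in the program that progressed patients carry the documented progression date.

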6.7 Imaging Regimen

Imaging is based on standard of care practices, although the following is highly recommended.

All patients with known disease below the head and neck will have at least a diagnostic CT scan of the chest, abdomen and pelvis (CAP) performed within 28 days before the initiation of study treatment, 9 \pm 1 weeks interval for the first two timepoints after initiation of treatment, and subsequent imaging performed at least every 12 \pm 1 weeks as per standard of care for radiologic and tumor measurement.

If the patient has known disease in the head and neck, the same protocol will apply with the addition of a head and neck CT within 28 days before the initiation of study treatment, 9 \pm 1 weeks interval for the first two timepoints after initiation of treatment, and subsequent imaging performed at least every 12 \pm 1 weeks as per standard of care.

Finally, for melanoma patients, an MRI of the brain will be performed 9 ± 1 weeks interval for the first two timepoints after initiation of treatment, and subsequent imaging performed at least every 12 ± 1 weeks as per standard of care.

The same method of assessment and the same technique should be used to characterize each identified and reported lesion pre-treatment and post-treatment.

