4.8.4. Duration of Stable Disease (DoSD)

The duration of stable disease is measured from the time measurement criteria are met for CR or PR or SD (whichever is first recorded) until the first date that recurrent or progressive disease is objectively documented or death, per RECIST v1.1 as determined by the investigator. Patients will be censored as PFS. DoSD (in months) is calculated as (event or censor date – first stable disease date + 1) / 30.4375.

DoSD analysis will be summarized based on Efficacy Population patients who had stable disease (CR or PR or SD). A summary of the number and percentage of patients experiencing an event, and the type of event (progression or death) will be provided along with median DoSD and Kaplan-Meier estimates.

A Kaplan-Meier plot of DoSD will be presented by pooled dose.

Sponsor:	NeolimmuneTech, Inc.		
Protocol:	NIT-106 (ION-02)		
Document Version No.:	1.0	Document Date:	20Nov2023

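### SAP Table 1 does not rank its day-1 censoring row for a deficient baseline against its event rows, and the same row gives DoSD a censor date before its start

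*SAP*

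**What the plan says.** SAP 4.8.2 defines the endpoint in the usual way: "PFS is defined as the time from C1/D1 to the first occurrence of progression or death from any cause, whichever occurs first". The sentence introducing Table 1 censors only patients without a known event: "Patients who are not known to have progressed prior to analysis cut-off date will be censored at the date of last adequate tumor assessment", or at the clinical cut-off if that comes first.

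The first row of Table 1, "Incomplete or no baseline tumor assessment", sets the date to C1/D1 and the outcome to censored. The Documented progression row uses "Earliest date on which radiological progression is documented" and the Death row uses the date of death; both give the outcome progressed. None of these rows refers to another, and neither the table nor the text ranks them. The SAP does not define *incomplete*.

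SAP 4.8.4 starts the DoSD clock at the first CR, PR or SD and then says only "Patients will be censored as PFS". The Efficacy Population (SAP 3.1.2) requires one cycle of treatment and one evaluable post-baseline assessment, but not a complete baseline. SAP 4.8.1 makes patients with no baseline assessment not evaluable for best response and does not mention an incomplete one.

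**The concern.** Death can be observed without a baseline scan, so there is no measurement reason to censor it on day 1. A patient with a deficient baseline who later dies or progresses satisfies two rows with opposite outcomes. Two programmers following the SAP could code that patient differently.

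If the first row wins, real events leave the PFS curve at day 1. Should patients with a poorer work-up also do worse, PFS is biased upward. If they do not, precision is still lost.

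DoSD has a separate fault. It borrows a censor date set for a clock that starts at C1/D1 and applies it to a clock that starts weeks later. Under SAP section 5, DoSD replaces duration of response, so it is the only duration-of-benefit analysis left. One patient could count toward disease control, contribute one day to PFS and have a negative DoSD.

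**Working it through.** The documents state no event count, power or precision for PFS or DoSD, so there is no plan figure to reproduce. The check applies the SAP's own formulas to illustrative patients.

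**Inputs**
- PFS: "PFS (in months) is calculated as (death or censor date – date of C1/D1 + 1) / 30.4375" (SAP 4.8.2).
- DoSD in months: event or censor date, minus first CR/PR/SD date, plus 1, over 30.4375 (SAP 4.8.4).
- First on-study tumor assessment: week 9, plus or minus 1 week (Protocol 6.7 and 11.1).

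**PFS when the first row is applied**
- Censored at C1/D1: (0 + 1)/30.4375 = 0.033 months.
- The same patient with an event at week 18 kept: (126 + 1)/30.4375 = 4.17 months.

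**DoSD when the censor date is C1/D1**

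| First CR/PR/SD | Calculation | DoSD (months) |
|---|---|---|
| Week 8 | (0 - 56 + 1)/30.4375 | -1.81 |
| Week 9 | (0 - 63 + 1)/30.4375 | -2.04 |
| Week 10 | (0 - 70 + 1)/30.4375 | -2.27 |

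The result is negative whenever the first CR/PR/SD is 2 or more days after C1/D1, so it is always negative on the planned schedule.

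**Does this depend on row order?** Suppose every event row outranks the first row. An event-free patient with an incomplete baseline is still sent to C1/D1. Only ranking the first row below the No progression row as well would avoid this. The first row would then have almost nothing left to do, because every Efficacy Population patient has a post-baseline assessment.

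One limit applies. Table 1 also counts treatment discontinuation as an event. If that row outranks the first row too, the affected patients are those still on treatment at cut-off.

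**Possible PFS bias if the first row wins.** Let q be the share of patients affected. Censoring them on day 1 means the curve estimates S_rest(t) instead of (1 - q)·S_rest(t) + q·S_inc(t), so the overstatement is q·[S_rest(t) - S_inc(t)]. The documents give neither q nor the medians. I assume exponential curves, q of 5, 10 or 20%, medians of 4 or 6 months in the rest and 2 or 3 months in those affected. At 6 months S = 2^(-6/median), which is 0.125, 0.250, 0.354 and 0.500 for medians of 2, 3, 4 and 6.

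| Medians (rest vs affected) | Difference in S(6) | q = 5% | q = 10% | q = 20% |
|---|---|---|---|---|
| 4 vs 3 | 0.104 | 0.5 | 1.0 | 2.1 |
| 4 vs 2 | 0.229 | 1.1 | 2.3 | 4.6 |
| 6 vs 3 | 0.250 | 1.3 | 2.5 | 5.0 |
| 6 vs 2 | 0.375 | 1.9 | 3.8 | 7.5 |

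The last three columns are percentage points. With equal prognosis the difference is zero, and the standard error rises by roughly 1/√(1 - q) = 1.03, 1.05 and 1.12.

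**The case against.** A reader might infer that the SAP deletes known PFS events. The documents do not settle that. The two event rows, the PFS definition and the sentence above the table all make such a patient an event. Deletion is one literal reading of one row; the firm defect is the missing order.

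A reader might also infer that incomplete baselines are common, because Protocol 6.7 says "Imaging is based on standard of care practices, although the following is highly recommended". But Protocol section 10 and SAP 2.4 both require scans within 28 days before treatment, measurable disease is an entry criterion, and eligibility waivers are barred. Entry by clinical examination does not make a baseline incomplete, since superficial lesions of at least 10 mm by calipers are measurable. One route to a larger number exists: Protocol 6.7 schedules on-treatment brain MRI for melanoma but states no pre-treatment one, and melanoma is 12 of the 60 planned Phase 2a patients (20%). That matters only if an unimaged brain counts as incomplete, which the SAP does not say.

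The negative DoSD has a narrow scope. Patients with no baseline are not evaluable for response and never enter DoSD. If *incomplete* means too deficient for any RECIST assessment, no CR, PR or SD could be assigned and the problem would not arise.

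The bias figures rest on assumption. A 2-month median puts about 51% of events before week 9, whereas this population requires an evaluable post-baseline assessment, so the larger values are doubtful.

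Finally, PFS is secondary, no p-values are planned, the study closed early and tumor assessments are listed by patient. All of this lowers the stakes. It does not supply a row order or make a negative duration valid.

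**Conclusion.** The point holds as an unresolved conflict in Table 1 together with a definite fault in DoSD censoring.

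- **PFS.** If the first row is applied as printed, a known death or progression becomes a censored time of 0.033 months. Under the assumed medians, 6-month PFS is then overstated by 0.5 to 1.9 points (5% affected), 1.0 to 3.8 points (10%) or 2.1 to 7.5 points (20%). There is no bias if prognosis is equal, and no events are lost if the event rows govern.
- **DoSD.** An event-free patient with an incomplete baseline and a recorded CR, PR or SD gets -1.81 to -2.27 months over weeks 8 to 10. That is not a valid Kaplan-Meier time. It does not depend on how the first row ranks against the event rows.

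The number of such patients is not in the documents and is probably small, possibly zero. The documents do not support saying that the plan systematically discards PFS events, or that PFS is materially biased. They do support correcting the rule, because the SAP is the basis for the study report and, with early closure, each patient carries more weight.

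**What to change.** In SAP 4.8.2:
- Define *incomplete* baseline.
- State that death is always a PFS event, and that documented progression is an event where it can be assessed against the recorded baseline lesions. Both override the first row.
- Limit C1/D1 censoring to patients with no usable baseline and no death.
- Censor other event-free patients at the last adequate assessment.
- Footnote the number of patients with a deficient baseline.
- Keep the printed rule as a sensitivity analysis for PFS only.

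In SAP 4.8.4, set the DoSD censor date no earlier than the first CR, PR or SD date. For the illustrative patient with SD at week 9 and a last adequate assessment at week 18, DoSD becomes (126 - 63 + 1)/30.4375 = 2.10 months.

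The cost is one table row, a sentence in each section and minor programming. The downside is that some progressions judged against a partial baseline will be less certain, notably new lesions in a region not imaged before treatment. The SAP should say how those are handled, and the footnote shows how many patients could be concerned.

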3. OBJECTIVES AND ENDPOINTS

This study will evaluate the safety and tolerability and assess the antitumor efficacy of NT-I7 in combination with atezolizumab (Phase 1b/2a) in patients with anti-PD-1/PD-L1 naïve or relapsed/refractory high-risk skin cancers (cSCC, MCC, melanoma). Specific objectives and corresponding endpoints for the study are outlined in Table 2.

Table 2 – Study Objectives and Endpoints

Objectives	Corresponding Endpoints
Primary Objective	

To evaluate the safety and tolerability of NT-I7 in combination with atezolizumab (Phase 1b), including estimation of the Maximum Tolerated Dose (MTD) and/or the Recommended Phase 2 Dose (RP2D)
 
Phase 2a: To evaluate the Objective Response Rate (ORR) according to RECIST v1.1 and iRECIST, as determined by the investigator
	
 - Incidence, nature, and severity of adverse events graded according to NCI CTCAE v5.0 - Incidence and nature of DLTs - Potential correlation with PK, pharmacodynamic, safety, and efficacy parameters - Objective Response Rate (ORR), defined as the percentage of patients who have at least one confirmed partial response (PR) or complete response (CR) according to RECIST v1.1 and iRECIST, as determined by the investigator
Secondary Objectives	

To evaluate immunogenicity of NT-I7 in combination with atezolizumab
 
To make a preliminary assessment of the anti-tumor activity of NT-I7 in combination with atezolizumab
	
 - Incidence of anti-drug antibody (ADA) to NT-I7 during the study relative to the prevalence of ADA at baseline - Disease Control Rate (DCR), defined as proportion of patients with a best overall response of CR, PR or stable disease (SD). - Duration of objective response (DOR), defined as the time from the first occurrence of a documented objective response to the time of the first documented disease progression or death from any cause, whichever occurs first, per RECIST v1.1 and iRECIST as determined by the investigator - Progression Free Survival (PFS), defined as the time from the first study treatment (Cycle 1, Day 1) to the first occurrence of progression or death from any cause, whichever occurs first, per RECIST v1.1 and iRECIST as determined by the investigator - Overall survival (OS), defined as the time from first study treatment (Cycle 1, Day 1) to death from any cause
Exploratory Objectives	

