11.1.4.3 Evaluation of Best Overall Response

The best overall response is the best response recorded from the start of the treatment until disease progression/recurrence (taking as reference for progressive disease the smallest measurements recorded since the treatment started). The patient's best response assignment will depend on the achievement of both measurement and confirmation criteria.

For Patients with Measurable Disease (i.e., Target Disease)

Target Lesions	Non-Target Lesions	New Lesions	Overall Response	Best Overall Response when Confirmation is Required*
CR	CR	No	CR	>4 wks. Confirmation**
CR	Non-CR/Non-PD	No	PR	>4 wks. Confirmation**
CR	Not evaluated	No	PR	
PR	Non-CR/Non-PD/not evaluated	No	PR	
SD	Non-CR/Non-PD/not evaluated	No	SD	Documented at least once >4 wks. from baseline**
PD	Any	Yes or No	PD	no prior SD, PR, or CR

Any	PD***	Yes or No	PD	
Any	Any	Yes	PD	

* See RECIST 1.1 manuscript for further details on what is evidence of a new lesion. ** Only for non-randomized trials with response as primary endpoint. *** In exceptional circumstances, unequivocal progression in non-target lesions may be accepted as disease progression. Note: Patients with a global deterioration of health status requiring discontinuation of treatment without objective evidence of disease progression at that time should be reported as “symptomatic deterioration.” Every effort should be made to document the objective progression even after discontinuation of treatment.
				

Abbreviations: CR=complete response; PD=progressive disease; PR=partial response; RECIST=Response Evaluation Criteria in Solid Tumors; SD=stable disease.

For Patients with Non-Measurable Disease (i.e., Non-Target Disease)

Non-Target Lesions	New Lesions	Overall Response
CR	No	CR
Non-CR/non-PD	No	Non-CR/non-PD*
Not all evaluated	No	not evaluated
Unequivocal PD	Yes or No	PD
Any	Yes	PD

*‘Non-CR/non-PD’ is preferred over ‘stable disease’ for non-target disease since SD is increasingly used as an endpoint for assessment of efficacy in some trials so to assign this category when no lesions can be measured is not advised
		

Abbreviations: CR=complete response; PD=progressive disease; SD=stable disease.

11.1.5 *iRECIST Response Assessment*

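### SAP Table 1 counts every treatment discontinuation as a PFS progression event, against the PFS definition and the censoring rule in the same section

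*SAP*

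**What the plan says.** The PFS definition is the same throughout. Protocol section 3 (Table 2) runs from first treatment "to the first occurrence of progression or death from any cause, whichever occurs first". Protocol 11.1.7 says "PFS is defined as the duration of time from start of treatment to time of progression or death, whichever occurs first". SAP 2.5.1 says "the time from the first study treatment to the first occurrence of progression, as measured by RECIST v.1.1 or death from any cause". SAP 4.8.2 repeats the same two events, and its planned event summary has only two types, progression and death.

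On censoring, SAP 4.8.2 states: "Patients who are not known to have progressed prior to analysis cut-off date will be censored at the date of last adequate tumor assessment", or at the clinical cut-off if that is earlier. Table 1 agrees in one row: "No progression Date of last adequate tumor assessment with no documented progression Censored". Its last row then reads "Treatment discontinuation Date of Treatment discontinuation Progressed". It names no reason for discontinuation, and nothing says which row prevails when two apply.

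The calculation line in the same section is "PFS (in months) is calculated as (death or censor date – date of C1/D1 + 1) / 30.4375". It does not mention the progression date.

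**The concern.** Stopping treatment is not progression. Protocol 6.4 lists many other grounds for stopping: intercurrent illness, adverse events, withdrawal, noncompliance, pregnancy, termination by the sponsor, and the physician's option to stop after a confirmed complete response. Under the last row, each of these becomes a progression on the stop date.

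That would turn PFS into a time-to-treatment-failure measure under a PFS label, and it would discard scans the protocol asks for. Protocol 6.6 keeps scanning patients who stop without RECIST progression, every 12 weeks for up to 12 months. The PFS curve and the landmark rates planned in SAP 4.8 (3, 6, 9, 12, 18 and 24 months) would be too low. The matter is live because SAP section 5 says the study closed prematurely, so patients on treatment at closure could be coded as progressed.

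**Working it through.** **1. Two rows, one patient.** Assume no progression at the week-9 scan, a stop for an adverse event at week 12, and no later scan. With the SAP month formula:
- Discontinuation row: progressed at (84 + 1)/30.4375 = 2.79 months.
- No-progression row: censored at (63 + 1)/30.4375 = 2.10 months.

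Outcome and date both differ, and the SAP gives no rule for choosing.

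**2. Narrower readings.**
- *Discontinuation due to progression.* The documented-progression row already covers this with the earliest radiological date. Protocol 6.4 lets stable patients stay on treatment past a first progression, so the discontinuation date can be later. If the earliest event is used, the row then does nothing.
- *Clinical progression.* The row does not say so. The note to the best-overall-response table (Protocol 11.1.4.3) says that global deterioration requiring "discontinuation of treatment without objective evidence of disease progression at that time should be reported as" symptomatic deterioration, and asks for objective progression to be documented afterwards.

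**3. Size.** The documents contain no PFS median, event count or discontinuation rate, so there is no figure to reproduce.

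*From the documents:* scans at weeks 9 and 18, then every 12 weeks (Protocol 11.1); months of 30.4375 days.

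*Assumed:* exponential progression with median m, so λ = ln 2/m; independent non-progression stops at hazard rλ.

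*Formulas:* let s be the elapsed time in months to the last scan recorded by time t.
- PFS as defined: S(t) = exp(−λs).
- With the row: S(t) × exp(−rλt).

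For m = 6, λ = 0.1155.
- At 6 months the last scan is week 18, s = 126/30.4375 = 4.14, and S = exp(−0.478) = 62.0%.
- At 12 months it is week 42, s = 294/30.4375 = 9.66, and S = exp(−1.116) = 32.8%.

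| r | 6-month PFS | 12-month PFS | Median (months) |
|---|---|---|---|
| 0 (as defined) | 62.0% | 32.8% | 6.9 |
| 0.10 | 57.8% | 28.5% | 6.9 |
| 0.25 | 52.1% | 23.2% | 6.9 |
| 0.50 | 43.8% | 16.4% | 4.2 |

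The median tends to fall on a scan date, so it moves only in the last case.

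Other medians, r = 0.25:
- m = 4: 12-month PFS 18.8% to 11.2%, median unchanged at 4.2.
- m = 9: 12-month PFS 47.5% to 37.7%, median 9.7 to 8.4.

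Ignoring the scan schedule, a 12-month PFS of 25% becomes 0.25^1.25 = 17.7% at r = 0.25.

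**4. Early closure.** In a simulation of 60 patients (600 replicates; assumed median 6 months, 10% of first exits being non-progression stops), closure was assumed uniform over 2 to 24 months per patient and coded as discontinuation. Mean 12-month PFS fell from 0.33 to 0.15, and events rose from 39.9 to 60.0 of 60.

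**5. The 24-month rate.** Treatment is capped at 2 years. The last three-weekly Day 1 within 730 days is Day 1 + 34 × 21 = 715, or 715/30.4375 = 23.49 months. If completing treatment counts as discontinuation and is dated at the last dose, nobody can be progression-free at 24 months. If it is dated at a visit 30 days later (Day 745, 24.48 months), this does not happen.

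**The case against.** **PFS decides nothing here.** It is a descriptive secondary endpoint, no p-values are planned, and no decision rule uses it. This is true and limits the consequences. It does not tell a programmer which of two incompatible rows to apply.

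**Read as due to progression, the row is harmless.** This also holds if the earliest event is used. But the text does not say it, and a row that is harmless only under an unstated restriction still needs correcting.

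**Censoring may be the more biased choice.** This is the strongest point. If patients stop because they are deteriorating and have no later scan, censoring is informative and biases PFS upward. Taking m = 6 and r = 0.25 with no later scans:
- Half of those who stop would progress before the next scan: 12-month PFS is 28.7% had scans continued, 32.7% with censoring (error +4.0 points) and 23.2% with the row (−5.5).
- All would: 24.9%, against 32.9% (+8.0) and 23.3% (−1.6). The row is then closer.

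This stands as a reason for a sensitivity analysis. It does not justify labelling adverse-event stops or complete responders as progressed.

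**The illustration overstates the effect.** PFS uses the Efficacy Population, which requires a post-baseline tumour assessment, so some early stoppers are excluded. Counting stops only after week 9 gives a 12-month rate of 24.6% rather than 23.2% at r = 0.25. The effect shrinks but remains. In a small sample the row can also put the curve slightly higher between a patient's last scan and stop date.

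**Absence from SAP section 5 proves little**, because the protocol has no censoring table to depart from. That is fair, and the finding does not depend on it.

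**Conclusion.** The concern holds. SAP 4.8.2 contradicts itself and the PFS definition in both documents, and the event definition must be settled before PFS is programmed. The contradiction is established from the text alone.

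The downward direction applies to patients who stop before documented progression or death. Its size rests on assumed medians, stop rates and exponential times. Across the 6-month-median scenarios without early closure, the loss at 12 months is 4.3 to 16.4 percentage points (32.8 − 28.5 and 32.8 − 16.4). The median may not move. The early-closure and 24-month effects depend on how closure and completion are coded. No hypothesis test, response-rate result or sample size is affected.

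The missing progression date in the PFS formula is a wording slip. Carry-over to duration of stable disease is doubtful, since SAP 4.8.4 borrows only the PFS censoring and names its own events.

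**What to change.** - Delete the treatment-discontinuation row from Table 1.
- For discontinuation without progression, use any post-treatment scans collected under Protocol 6.6; otherwise censor at the last adequate tumour assessment.
- Correct the formula to (progression, death or censor date − C1/D1 + 1)/30.4375.
- State in SAP 4.8.4 that discontinuation is not an event for duration of stable disease.
- Report time to discontinuation, progression or death under its own label as a sensitivity analysis, with the number of non-progression discontinuations by reason.

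The cost is SAP wording and programming. Discontinuation reasons and dates are already recorded (Protocol 6.4) and reasons are tabulated (SAP 4.4). The price is more censoring, wider intervals and possible upward bias from informative stopping, which the sensitivity analysis makes visible.
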